7.5.2 Secondary Safety Variables

Adverse events

AEs will be coded according to the Medical Dictionary for Regulatory Activities (MedDRA, version 21.0). For MP, only treatment emergent adverse events (TEAEs) of the MP will be analyzed, which are defined as AEs with onset or worsening on or after date and time of the first MP administration and before date and time of the first OLEX administration at V6. For subjects who do not receive an OLEX administration all AEs with onset or worsening on or after date and time of the first MP administration will be considered as TEAEs of MP. TEAEs of the OLEX are defined as AEs with onset or worsening at or after date and time of the first OLEX administration at V6. TEAEs will be allocated to an injection cycle x in the OLEX Period, if adverse events has onset or worsening on or after injection x and before injection x+1 (if applicable). TEAEs of the OLEX will be analyzed in total and per treatment cycle. Additionally TEAEs of the MP and the OLEX period will be displayed together in total.

Only TEAEs will be analyzed. Non-TEAEs will only be listed.

If an AE worsens between start and end of this AE it will be considered as new AE starting with the date of the worsening. In this case the imputation of end dates within episodes of the

same AE will be done by setting the end date/end time to start date/start time of the consecutive worsening record.

In detail missing or partially missing start and stop dates of an AE will be imputed as follows for the calculation of the duration of an AE:

- if start time is missing and start date is given and not equal to date of an injection visit, set start time to 00:00, else if start date is equal to date of an injection visit set start time to time of injection, if given (else 00:00)
- if start date/time is completely missing and end date is before first exposure in the MP: no imputation
- if start date/time is (partially) missing and end date after or equal first exposure in the MP or missing:
 - only start day is missing, but start month and start year same as an injection visit: set start day and start time to day and time of this injection visit, else set start day to 1 and start time to 00:00
 - start day and start month are missing, but start year is the same as year of first exposure in the MP: set start day, start month, start time to day, month, time of first exposure in the MP, else set start day and start month to 1 and start time to 00:00

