 - start date/time completely missing and end date/time not before date/time of first exposure in the MP, set start date/time to date/time of first exposure in the MP
 - if AE end date and time are missing set end date to study end date (i.e. last contact or last visit of the study) and end time to 23:59
 - if AE end date/time is partially missing, set end day to last day of the given month or end day/month to 31/12 of the given end year and missing end time to 23:59
 - if AE end time is missing set time to 23:59.

Imputation rules for multiple records in case of AE worsening:

- For missing AE start date/time the imputation strategies as defined above will be applied to all records of the same AE.
- For missing TEAE end date/time the imputation strategies as defined above will be applied to the last record of the same TEAE.

Calculation of time to onset/duration of AEs [days]:

- Time to onset of an AE is defined as start date of AE - date of most recent administration of study drug [+ 1 for AE starting after start of treatment]
- The duration will be calculated as stop date - onset date + 1 for each episode of worsening.

Incidences will be calculated for TEAEs overall (MP+OLEX), overall OLEX and by injection cycle on the system organ class (SOC) level and on the preferred term (PT) level (i.e., total, by worst intensity, by worst relationship, and by worst outcome). Listings and, if applicable, tables displaying incidences for TEAEs leading to discontinuation, serious TEAEs, related serious TEAEs, TEAEs of special interest, and deaths will also be provided. Additionally the number and percentage of subjects with at least one non-serious TEAE with incidence $\geq 5\%$

in any MP treatment group or in the OLEX Period and number of non-serious TEAE will be displayed by SOC level and PT level. Time to onset and duration of AEs will be listed. Time to onset and duration of AEs will be listed.

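### The rule for adverse events with a missing start day does not check the end date against the re-injection visits, so an event can be given a start after its known end

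*SAP*

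**What the plan says.** All the rules are in SAP section 7.5.2, under adverse events.

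- **Start with only the day missing.** If month and year match an injection visit: "start month and start year same as an injection visit: set start day and start time to day and time of this injection visit". If they match none, the start becomes day 1 of the month.
- **Condition on the rule.** It sits under one parent condition: "if start date/time is (partially) missing and end date after or equal first exposure in the MP or missing". First exposure in the main period (MP) is V2. The section contains no comparison of the end date with V6, V10 or V14, and none of the imputed start with the event's own end.
- **Stated purpose.** The dates are "imputed as follows for the calculation of the duration of an AE".
- **Duration.** "The duration will be calculated as stop date - onset date + 1 for each episode of worsening". Time to onset is counted from the most recent administration before the start.
- **Partial end dates.** "if AE end date/time is partially missing, set end day to last day of the given month".
- **Period and cycle.** A treatment-emergent event of the MP must begin "before date and time of the first OLEX administration at V6". For the open-label extension (OLEX), "TEAEs of the OLEX are defined as AEs with onset or worsening at or after date and time of the first OLEX administration". Within OLEX, "TEAEs will be allocated to an injection cycle x in the OLEX Period" according to whether it begins on or after injection x and before the next one.

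**The concern.** The rule can apply to four injections, but its end-date safeguard was written for one. At V2 the safeguard works, because an event that ended before V2 never reaches the rule. At the three re-injections nothing stops the rule from overriding a known end date. Duration and time to onset are then impossible or wrong for that event.

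There is a second, conditional consequence. Period and cycle are decided by onset, and an onset set exactly to the V6 time falls in OLEX by definition. If the imputed dates are used for that decision, an event that began and ended under the blinded MP dose leaves the MP tables and is reported after open-label high-dose treatment. The MP is the only randomised comparison of doses for safety.

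**Working it through.** The documents state no figure on this point, so there is none to reproduce. The check applies the rule as written to dated cases.

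**Inputs.** The rules are those above. The dates are illustrative, with 14-week cycles (the plan allows 12 to 16 weeks): V2 on 12 Feb 2016, V6 on 20 May 2016, V10 on 26 Aug 2016. At this spacing no calendar month holds two planned injections.

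**Formula.** Duration = stop date - onset date + 1.

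| Start recorded | End | Imputed start | Duration (days) | Period by imputed start |
|---|---|---|---|---|
| Feb 2016 (V2 month) | 20 Feb | 12 Feb | 20 - 12 + 1 = 9 | MP, no fault |
| Apr 2016 (no injection) | 10 Apr | 1 Apr | 10 - 1 + 1 = 10 | MP, no fault |
| May 2016 (V6 month) | 10 May | 20 May | 10 - 20 + 1 = -9 | OLEX, though over before V6 |
| Aug 2016 (V10 month) | 21 Aug | 26 Aug | 21 - 26 + 1 = -4 | Cycle begun at V10, though over before V10 |

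**General result.** If the known end is at least one day before the re-injection, stop - onset is at most -1, so the duration is at most 0.

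**Time to onset.** In the May case the most recent administration before the imputed start is V6 itself, so the result is 0 days (1 with the SAP's added day). The true onset lay between 1 and 10 May, which is 79 to 88 days after V2.

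**What the reversal requires.** The start day is unknown, the start month contains V6, V10 or V14, and the end is known to fall before that injection. A partly missing end date goes to the end of its month or year, so it cannot precede an injection in the start month. The end must be recorded to the day, or be taken from the start of a later worsening record of the same event.

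**How often, given a missing start day in a V6 month.** The documents give nothing here, so this rests on assumptions: a 30-day month, V6 day and true onset day each uniform and independent, and a true duration of L days. Of the 30 x 30 = 900 day pairs, those with the end before V6 number (30 - L)(31 - L)/2.

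| L (days) | Pairs | Share of 900 |
|---|---|---|
| 1 | 435 | 48% |
| 3 | 378 | 42% |
| 5 | 325 | 36% |
| 7 | 276 | 31% |
| 14 | 136 | 15% |

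These shares apply only to events whose start day is missing in such a month. They are not shares of all adverse events.

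**The case against.** **The dates are for duration only.** This has force. The SAP introduces the imputation for that purpose, and section 7.5.2 says duration and time to onset will be listed. A reader might infer that affected events are certain to be counted as open-label events. The documents do not support that: they never say that imputed dates feed period or cycle allocation. It is a plausible reading, because no other rule for partial start dates exists, but it remains an inference. The impossible duration needs no inference.

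**It is rare.** Probably so. Date of onset is a required item (protocol section 10.1). Events are asked about at every visit and contact, including before each injection (section 9.1.1.6). Queries are resolved before the MP database closes (section 11.3). Serious events and events of special interest are reported within 24 hours of knowledge (sections 10.2 and 10.3). These steps make the trigger uncommon, but they do not repair the rule.

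**Little depends on it.** Safety is descriptive and has no primary variable. The rule is the same in every arm, and nothing shows a bias between doses. MP and OLEX events are also shown together in total, and OLEX tables are split by MP dose group, so no event is lost. All of this stands and limits the weight of the point.

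**It is a worst-case convention.** SAP section 7.5.2 applies a worst-case strategy to missing adverse event data, spelling it out for intensity, causal relationship and outcome. Placing an onset at an injection is defensible when the end is missing or later. It is not when the event is known to have ended first.

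**Not every event that began before the injection is an error.** A reader might infer that about half of day-missing events in a re-injection month are misplaced, since 435/900 = 48% begin before V6 under uniform dates. That count includes events still continuing at the injection. For those, and for events with no end date, the injection day is a convention that the fix below keeps. It does not measure this fault.

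**Conclusion.** The rule is wrong as written for V6, V10 and V14. Whenever it meets an event with a known end before the injection in the same month, it returns a start after the end, a duration of zero or less, and a wrong time to onset. V2 is protected.

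Movement from MP to OLEX, or to the next OLEX cycle, follows only if the imputed dates are used for allocation. The SAP leaves that open, which is a gap in itself.

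The number of events is not given and is probably small. The shares of 15% to 48% rest on assumed uniform dates and assumed durations of 14 days down to 1 day, and apply only within a group of unknown size. The outputs affected are descriptive safety listings and, on the conditional reading, the MP and OLEX event tables. No confirmatory result is touched.

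**What to change.** In SAP section 7.5.2, for a start with only the day missing in the month of an injection:

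1. Set the start to the injection day and time only if the end date is missing or is on or after that injection.
2. Otherwise set it to the later of day 1 of the month and the previous injection date, and never later than the end date.
3. State that these same dates decide MP/OLEX and cycle allocation.

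In the May case the start becomes 1 May, the duration 10 - 1 + 1 = 10 days, and the event stays in the MP. In the August case the start becomes 1 August, the duration 21 - 1 + 1 = 21 days, and the event stays in the cycle begun at V6. Day 1 is already the SAP's default for months without an injection, so no new convention is introduced.

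The cost is one amended SAP line, one added sentence and one programming condition. No new data are needed.

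### SAP 7.5.2 imputes worsening dates without checking them against the event's own onset, so a worsening can be dated before the event it worsens

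*SAP*

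**What the plan says.** All of the following is in SAP 7.5.2.

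- **Status of a worsening.** "If an AE worsens between start and end of this AE it will be considered as new AE starting with the date of the worsening". Where an AE has several episodes, the end of an episode is set to the start of the next worsening record.
- **Rule for incomplete worsening dates.** "For missing AE start date/time the imputation strategies as defined above will be applied to all records of the same AE". The rules referred to are those for any AE:
  - Day missing: the rule first covers the case "only start day is missing, but start month and start year same as an injection visit", and the start becomes that injection. Otherwise it becomes day 1 of the month at 00:00.
  - Day and month missing: where "start day and start month are missing, but start year is the same as year of first exposure in the MP", the start becomes first MP exposure. For any other year it becomes 1 January.
  - Whole date missing: "start date/time completely missing and end date/time not before date/time of first exposure in the MP, set start date/time to date/time of first exposure".
- **Only date check.** The rules ask whether the end date lies before first MP exposure.
- **Stated purpose.** The rules are introduced as serving the computation of AE duration. TEAE allocation is not named.
- **Period windows.** An MP TEAE has onset or worsening from the first MP injection until before the first OLEX injection (V6), by date and time.
- **End dates.** A fully missing end date becomes the study end date. For a partly missing one the rule is to "set end day to last day of the given month or end day/month to 31/12 of the given end year", with no cap.

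SAP 7.5 tabulates MP safety data by MP dose group as treated.

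**The concern.** A worsening cannot precede the event it worsens. The rules were written for isolated AEs. There, defaulting to first exposure is a reasonable choice when it is unknown whether the event is treatment-emergent. For a worsening record the onset of the parent event is usually known, and the rules ignore it.

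Two things are at stake. The first is certain: impossible sequences and negative durations in the AE listings. The second is conditional. If imputed dates decide whether a record belongs to MP or to an OLEX cycle, an episode that happened on open-label high-dose treatment can be counted under the subject's blinded dose group, which may be low or mid. The record may carry a higher intensity, so the worst-intensity tables are affected too, and the OLEX cycle loses that episode.

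**Working it through.** The documents give no figure on this point, so there is nothing to reproduce. The check applies the rules literally.

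**Inputs.** Start-date, end-date and duration rules and TEAE windows: SAP 7.5.2. Group sizes 172 / 86 / 86 and high-dose treatment in OLEX: SAP 3.1. Duration = stop date - onset date + 1: SAP 7.5.2. The calendar dates below are assumed.

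**Example 1, year only.** V2 12 Jan 2016, V6 19 Apr, V10 26 Jul. A mild AE starts 3 Aug, worsens to severe on a date recorded only as 2016, and ends 20 Sep.

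1. The recorded year equals the year of first exposure, so the worsening is dated 12 Jan 2016.
2. 3 Aug - 12 Jan = 204 days before the AE began.
3. The first episode ends at the imputed start: 12 Jan - 3 Aug + 1 = -203 days.
4. The severe episode lasts 20 Sep - 12 Jan + 1 = 253 days.
5. If imputed dates drive allocation, 12 Jan lies between V2 and V6, so the severe episode is an MP TEAE. The true event began 8 days after V10.

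**Example 2, day missing.** Same subject, AE onset 20 Aug, worsening recorded as Aug 2016, no injection in August. The imputed start is 1 Aug, and the first episode lasts 1 Aug - 20 Aug + 1 = -18 days. The record stays in OLEX.

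**Which missing dates can cross from OLEX into MP**

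- Wholly missing: always, because the start becomes V2.
- Year only: when the imputed value (V2, or 1 January of a later year) falls before V6.
- Month and year known: never. If the month contains V6, the start becomes V6. A later month gives another injection or day 1, both after V6.

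The rules were also run on 200,000 simulated subjects with onset and worsening both truly in OLEX. Assumptions: V2 uniform over three calendar years, cycles of 84-112 days, onset uniform over OLEX, worsening 1-28 days later.

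| Worsening date | Dated into MP | Dated before onset |
|---|---|---|
| Wholly missing | 100% | 100% |
| Year only | about 56% | about 96% |
| Month and year | 0% | about 44% |

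The 100% figures and the 0% follow from the rules. The other shares depend on the assumed calendar. All are shares of incomplete records, not of all AEs.

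**Effect of one misplaced subject on an MP row.** Mid or low: 1/86 = 1.16 points. High: 1/172 = 0.58 points.

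**End dates.** Suppose study end is 20 Sep 2016. An AE end recorded as 2016 becomes 31 Dec, 102 days after last contact (10 + 31 + 30 + 31). A fully missing end becomes 20 Sep. The record with more information gets the impossible date.

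**The case against.** **The rules are only for duration.** This is the strongest point, and it limits the claim. The SAP ties the imputation to duration, and durations are only listed. A reader might infer that the SAP directs open-label worsenings into the MP tables; no sentence says so. The negative durations stand even on this narrow reading. Allocation by imputed date remains the natural reading. Duration uses whole dates, yet the rules impute clock times down to the time of injection, which matters only for the TEAE windows. The SAP also offers no other way to place an undated record. If allocation is meant to work differently, that rule is missing.

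**Such records should be rare.** This stands. Protocol 10.1 makes the date of worsening a required AE item, AEs are asked about at every visit and telephone contact (9.1.1.6), and queries and monitoring precede database close (11.3, 11.4). The documents give no rate, so rarity is expected, not shown.

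**The effect on tables is limited.** This largely stands. If the subject already has the same preferred term in MP, the incidence does not change, although worst intensity, relationship or outcome may. The safety analysis is descriptive, and the combined MP and OLEX display still contains the episode. A reader might also speak of the randomised comparison being altered, but the MP safety tables are by dose group as treated.

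**The end-date point is separate.** Agreed. End dates do not place a TEAE in a period, so the missing cap affects listed durations only.

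**Conclusion.** The concern holds for what the text fixes. As written, SAP 7.5.2 can date a worsening before its own event and close the earlier episode before it began. That is a stated rule giving wrong output, not missing detail.

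Misplacement into the MP tables is conditional on imputed dates driving TEAE allocation. It is also confined to a wholly missing date, or a year-only date whose imputed value precedes V6. A reader might infer that any incomplete worsening date causes it; a known month and year does not. Each misplaced subject moves an MP row by at most about 1.2 points in the mid or low group, or 0.6 points in the high group.

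The confirmatory efficacy tests are untouched. The correction is worth making because it is cheap and the present output would be visibly impossible.

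**What to change.** 1. In SAP 7.5.2, replace the sentence on missing start dates of worsening records with: *For a worsening record, the imputed start is the later of (a) the date from the rules above and (b) the start date/time of the preceding record of the same AE, consistent with any recorded year or month and not later than the record's own end date.* In example 1 this gives 3 Aug 2016 (OLEX), and in example 2 it gives 20 Aug; the first episode then lasts 1 day in each.
2. Do not simply substitute the preceding record's start whenever the month or whole date is missing, because that can override a recorded year. Take V2 20 Sep 2016, V6 28 Dec 2016, onset in Nov 2016 and a worsening recorded as 2017. The present rule gives 1 Jan 2017, correctly in OLEX; substitution would give Nov 2016, in MP. Taking the later date keeps 1 Jan 2017.
3. State that imputed dates drive MP/OLEX and cycle allocation. The floor does not settle an event with MP onset and an undated worsening, so where the period is still ambiguous, use the visit at which the worsening was reported.
4. Cap partly missing end dates at the subject's study end date, as is done for fully missing ones.

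The cost is a few sentences of SAP text and a few lines of date-derivation code, provided that the visit of report can be identified from the recorded data.

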For any missing data of adverse events, a worst case strategy will be applied for all analysis tables. The intensity will be imputed by the worst intensity “severe”, the causal relationship will be imputed by the worst relationship “drug related”. Missing data of the worst outcome will be imputed by “unknown”. If a subject has more than one outcome within a preferred term (PT) only the worst outcome will be used in the frequency tables. Also on subject level only the worst outcome category per subject will be counted in the frequency table. The worst outcome is defined in the following order:

- recovered/resolved
- recovered/resolved with sequelae
- recovering/resolving
- not recovered/not resolved
- unknown
- fatal

TEAESIs are defined as TEAEs that are thought to possibly indicate toxin spread. A list of adverse events of special interest possibly indicating toxin spread is given in **Table 1: List of Adverse Events of Special Interest Possibly Indicating Toxin Spread.**

Table 1: List of Adverse Events of Special Interest Possibly Indicating Toxin Spread

MedDRA PT	MedDRA PT
Accommodation disorder	IIIrd nerve paresis
Areflexia	Ileus paralytic
Aspiration	IVth nerve paresis
Botulism	Monoparesis
Bradycardia	Muscular weakness
Bulbar palsy	Paralysis
Constipation	Paraparesis
Cranial nerve palsies multiple	Paresis
Cranial nerve paralysis	Paresis cranial nerve
Diaphragmatic paralysis	Peripheral nerve palsy
Diplopia	Peripheral paralysis
Dry mouth	Pelvic floor muscle weakness
Dysarthria	Pneumonia aspiration
Dysphagia	Pupillary reflex impaired
Dysphonia	Quadriparesis
Dyspnoea	Respiratory arrest
Extraocular muscle paresis	Respiratory depression
Eyelid function disorder	Respiratory failure
Eyelid ptosis	Speech disorder
Facial paralysis	Trigeminal nerve paresis
Facial paresis	Urinary retention
Hemiparesis	Vision blurred
Hypoglossal nerve paresis	Vocal cord paralysis
Hyporeflexia	Vocal cord paresis
Hypotonia	
Wording of PTs is according to MedDRA version 21.0	

To fulfill FDA requirements, TEAE data will be screened for suicidal events. The MedDRA PTs of all TEAEs will be checked using standard MedDRA query (SMQ) „Suicide/self-injury“. Resulting TEAE findings will be listed in a separate listing. A list of the MedDRA PTs of the SMQ „Suicide/self-injury is given in Table 2.

Table 2: List of Adverse Events of Standard MedDRA Query „Suicide/self-injury“

MedDRA PT:	MedDRA PT:
Columbia suicide severity rating scale abnormal	Self injurious behaviour

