Completed suicide	Self-injurious ideation
Depression suicidal	Suicidal behaviour
Intentional overdose	Suicidal ideation
Intentional self-injury	Suicide attempt
Poisoning deliberate	Suicide threat

In addition all comment fields of the case report form (CRF) and all investigator reported terms of TEAEs will be screened for the following terms or term elements (‘strings’) and listed in a separate listing:

Table 3: List of Search Terms and Search Strings of Possibly Suicidal Events

Term:	Term:
attempt	self inflict
cut	self injur
gas	self-damage
hang	self-harm
hung	self-inflict
jump	self-injur
mutilate	shoot
overdos	slash
self damage	suic
self harm	

Obvious false positive findings will be excluded from the listing (e.g., “gas” in “gastrointestinal” or “cut” in “acute” or in “cutaneous”).

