7.5.3 Other Safety Variables

Laboratory evaluations, vital signs, BMI, body weight, height, Investigator’s Global Assessment of Tolerability, and incidences of subjects with antibodies against BoNT-A will be analyzed descriptively (values and changes from baseline) and screened for individual notable values and/or changes. Results of the C-SSRS will be summarized descriptively.

The following analyses will be performed for the MP data:

C-SSRS

Additionally, to fulfill FDA requirements, prospective monitoring of suicidality with the C-SSRS should be considered the most important (but not the only) source of information concerning suicidality.

These C-SSRS assessments will be done in the subpopulation of subjects enrolled after amendment 1.0 approval only.

Suicidality will be assessed prospectively in subjects at baseline and all post-baseline visits. The appropriate version of this scale ensures the consistent application of this important measure regardless of indication or investigator experience with the subject matter. With C-SSRS in place, administration of this semi-structured clinician-based assessment scale is standardized. The C-SSRS quickly and efficiently identifies those subjects that require additional clinician follow up.

Following versions of the C-SSRS are to be applied only for subjects enrolled after amendment approval:

1. Children's baseline / screening version
2. Children's since last visit version.

The C-SSRS interview should only be assessed with children of respective age and cognitive state. Clear age cut-offs for the C-SSRS were not defined by the authors, but it has been found that administration is possible in general for children with a developmental age of about 7 years. Otherwise it should be documented in the eCRF that a child was not able to assess the C-SSRS at a respective visit.

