TEAE data and all CRF comments will be screened for possibly suicidal events. For this purpose an additional listing will be generated (see section 7.5.2).

Additionally, to fulfill FDA requirements, only for subjects of respective age and cognitive state enrolled after amendment 1 approval, prospective assessments for suicidality using the C-SSRS assessments have to be applied.

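### SAP Table 3 lists 'mutilate' in full rather than as a stem, so the suicidality text screen misses 'mutilation' and 'mutilating', mainly in uncoded CRF comments

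*SAP*

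**What the plan says.** SAP 7.5.2 describes two screens for suicidal events beyond ordinary adverse event reporting.

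- **Coded terms.** The preferred terms of all TEAEs are checked against the Suicide/self-injury SMQ. Its terms are listed in Table 2 and include 'Intentional self-injury' and 'Self injurious behaviour'.
- **Free text.** In addition, the comment fields of the CRF and "all investigator reported terms of TEAEs will be screened for the following terms or term elements" given in Table 3, titled "List of Search Terms and Search Strings of Possibly Suicidal Events". After the search, "Obvious false positive findings will be excluded from the listing"; the examples given are 'gas' found in 'gastrointestinal' and 'cut' found in 'acute' or 'cutaneous'.

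SAP 8 repeats the commitment: "TEAE data and all CRF comments will be screened for possibly suicidal events".

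SAP 7.5.3 describes the C-SSRS as the most important, though not the only, source on suicidality, and limits its use: "These C-SSRS assessments will be done in the subpopulation of subjects enrolled after amendment 1.0 approval only". It is further limited to children of suitable age and cognitive state.

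**The concern.** Table 3 is a list of text strings, and its value depends on each string catching the forms in which a word may be written. Most entries that need it are cut so that different endings match. 'mutilate' is not, so it catches 'mutilated' and 'mutilates' but not the noun or the '-ing' form. Because the entry is in the table, the sponsor evidently meant to capture this concept. The defect is a slip in carrying out a stated intention; no different list is being argued for.

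At stake is the completeness of a listing that SAP 7.5.2 introduces to meet an FDA requirement. It matters most for CRF comments, because this string search is the only suicidality screen that the SAP applies to them.

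**Working it through.** The plan gives no figure to reproduce. The check is a case-insensitive substring test of the Table 3 entries.

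**Inputs (SAP 7.5.2, Table 3), 19 entries:** attempt, cut, gas, hang, hung, jump, mutilate, overdos, self damage, self harm, self inflict, self injur, self-damage, self-harm, self-inflict, self-injur, shoot, slash, suic.

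**Step 1: the matching rule.** The SAP speaks of term elements and expects 'gas' to hit 'gastrointestinal' and 'cut' to hit 'acute' and 'cutaneous'. That happens only if an entry may match inside a word. The test reproduces all three of these hits.

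**Step 2: the stem design.** Under this rule 'overdos' finds 'overdose' and 'overdosing', 'suic' finds 'suicide' and 'suicidal', and 'self-injur' finds 'self-injury' and 'self-injurious'. The cut endings do their job.

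**Step 3: the entry at issue.** 'mutilate' is the only entry that begins 'mutilat'. The entries that begin with 'self' cover damage, harm, inflict and injur only.

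| Text | Entries that match now | Contains 'mutilat' |
|---|---|---|
| self-mutilation | none | yes |
| self mutilation | none | yes |
| mutilation | none | yes |
| mutilating | none | yes |
| self-mutilating behaviour | none | yes |
| automutilation | none | yes |
| self-mutilated | mutilate | yes |
| mutilates | mutilate | yes |
| self-mutilation by cutting | cut | yes |
| self-inflicted mutilation | self-inflict | yes |

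The first six texts show that the string fails on the noun and the '-ing' form. They were chosen to test that spelling point, so they are not an estimate of how often the trial's records would be missed. The last two show that such a text is still found when another listed string happens to be present.

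**Step 4: alternatives.** Whole-word matching would not help, since 'mutilate' is not a word within 'self-mutilation'. With the stem 'mutilat', all ten texts match. Because 'mutilat' is the beginning of 'mutilate', any text found by the longer string is also found by the shorter one.

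**Step 5: which source is exposed.** A reported TEAE term passes through two screens, the string search and the SMQ on its coded preferred term. A CRF comment passes through the string search only.

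**The case against.** The strongest reply is that very little depends on this entry.

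- **TEAE terms have a second screen.** A TEAE reported as self-mutilation would be coded, and Table 2 contains preferred terms to which it might be assigned. The documents do not say how it would be coded, so a missed TEAE is possible but not shown. A reader might infer that reported terms and comments are equally exposed; the SMQ check means that they are not.
- **Comments are not the only record.** Protocol 9.1.1.6 requires every observed AE to be documented in the eCRF, and Protocol 11.3 allows queries from source data verification and from medical or safety review. A self-injury event should therefore also appear as an AE. If it is treatment-emergent, it then reaches the SMQ check. The uncovered case is a comment with this wording, no other Table 3 string and no corresponding AE record.
- **The wording may be rare.** Table 3 already covers self-injury, self-harm, self-inflicted and self-damage, with a space and with a hyphen, as well as cut, slash and suic. A reader might infer that 'self-mutilation' is the usual way to write such an event. Nothing in the documents shows how investigators word it.
- **The C-SSRS is the main source.** A reader might infer that many children have no C-SSRS and depend on the text search. SAP 7.5.3 does restrict the C-SSRS by enrolment date, age and cognitive state, and the trial enrols from age 2. However, no number is given, and AE questioning and the SMQ check apply to every child.

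All of this stands as a limit on weight. None of it alters the string logic: the entry fails on the noun and the '-ing' form of the word it was put there to catch.

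**Conclusion.** The point holds as a small defect in the search rule. Followed as written, Table 3 misses 'mutilation' and 'mutilating' unless another listed string is in the same text, and this departs from the stem design used elsewhere in the table. The exposure is mainly in uncoded CRF comments. The number of affected entries is unknown and likely small. Only the supplementary suicidality listing is affected; no efficacy analysis, error rate or planned inference depends on it.

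Two assumptions are made. The search program is taken to implement substring matching as the SAP's examples imply, although whole-word matching would miss the same forms. The search is also taken to ignore letter case, which the SAP does not state and which does not affect the result.

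A reader might go further and conclude that self-injury events will go undetected in this trial. The documents do not support that, given the AE recording duty, the SMQ check and the C-SSRS.

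**What to change.** Replace 'mutilate' by the stem 'mutilat' in SAP Table 3 and in the search program. This deletes one character in each place. Extra false positives, if any, fall under the exclusion step that SAP 7.5.2 already provides. The documents do not say whether the list is the sponsor's own or was prescribed. If it was prescribed, adding 'mutilat' alongside the existing entry gives the same result.
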